5.7 Study Drug

For subjects receiving study drug, rovalpituzumab tesirine (0.3 mg/kg or adjusted dose) supplied by AbbVie will be administered intravenously (IV) once every 6 weeks beginning on Day 1 (day of dosing) for 2 doses (cycles) per subject in Study Arm A (Optional Retreatment) or once every 6 weeks beginning on Day 1 (day of dosing) omitting every third cycle until disease progression or study drug discontinuation in Study Arm B. Oral dexamethasone 8 mg (or alternative corticosteroid at equivalent

dosing) will be administered twice daily (BID) on Day –1, Day 1, and Day 2 for all subjects receiving rovalpituzumab tesirine.

AbbVie will not routinely supply drug other than rovalpituzumab tesirine. AbbVie will not routinely provide dexamethasone (or its equivalent) unless specified in operational or regulatory requirements (i.e., local site/country-specific requirements). Non-investigational medicinal product (standard of care) must be obtained commercially.

Instructions for drug preparation will be provided by AbbVie. Further details are provided in the Operations Manual, Section 6.

5.8 Randomization/Drug Assignment

As subjects are enrolled in the study, they will be classified into the 2 study arms (A or B), and will be given a unique subject identification number. Rovalpituzumab tesirine will be dispensed using an Interactive Response Technology (IRT) at the study visits, as summarized in Section 5.7, for subjects in Study Arm A (Optional Retreatment) or Study Arm B.

5.9 Protocol Deviations

The Investigator is responsible for complying with all protocol requirements, written instructions and applicable laws regarding protocol deviations. Protocol deviations are prohibited except when necessary to eliminate an immediate hazard to study subjects. If a protocol deviation occurs (or is identified), the Investigator is responsible for notifying IEC/IRB (as applicable), regulatory authorities (as applicable) and AbbVie.

6 SAFETY CONSIDERATIONS

6.1 Complaints and Adverse Events

Complaints

A complaint is any written, electronic, or oral communication that alleges deficiencies related to the physical characteristics, identity, quality, purity, potency, durability, reliability, safety, effectiveness, or performance of a product/device. Complaints associated with any component of this investigational product must be reported to AbbVie.

Medical Complaints/Adverse Events and Serious Adverse Events

An AE is defined as any untoward medical occurrence in a subject or clinical investigation subject administered a pharmaceutical product and which does not necessarily have a causal relationship with this treatment. An AE can therefore be any unfavorable and unintended sign (including an abnormal laboratory finding), symptom, or disease temporally associated with the use of a medicinal (investigational) product, whether or not the event is considered causally related to the use of the product.

The investigators will monitor each subject for clinical and laboratory evidence of adverse events on a routine basis throughout the study. All AEs will be followed to a satisfactory conclusion.

If an AE meets any of the following criteria, it is to be reported to AbbVie as a SAE within 24 hours of the site being made aware of the event:

Life-Threatening An event that, in the opinion of the investigator, would have resulted in

immediate fatality if medical intervention had not been taken. This does not include an event that would have been fatal if it had occurred in a

more severe form.

Hospitalization or Prolongation of Hospitalization An event that results in an admission to the hospital for any length of time or prolongs the subject's hospital stay. This does not include an emergency room visit, admission to an outpatient facility, respite, or

hospice care.

Congenital Anomaly An anomaly detected at or after birth or any anomaly that result in fetal

loss

Persistent or Significant Disability/Incapacity

An event that results in a condition that substantially interferes with the activities of daily living of a study subject. Disability is not intended to include experiences of relatively minor medical significance such as headache, nausea, vomiting, diarrhea, influenza, and accidental trauma (e.g., sprained ankle).

Important Medical Event Requiring Medical or Surgical Intervention to Prevent Serious Outcome An important medical event that may not be immediately life-threatening or result in death or hospitalization, but based on medical judgment may jeopardize the subject and may require medical or surgical intervention to prevent any of the outcomes listed above (i.e., death of subject, life-threatening, hospitalization, prolongation of hospitalization, congenital anomaly, or persistent or significant disability/incapacity). Additionally, any elective or spontaneous abortion or stillbirth is considered an important medical event. Examples of such events include allergic bronchospasm requiring intensive treatment in an emergency room or at home, blood dyscrasias or convulsions that do not result in inpatient hospitalization, or the development of drug dependency or drug abuse.

Further details on AEs and SAE are provided in the Operations Manual, Section 4.

AbbVie will be responsible for Suspected Unexpected Serious Adverse Reactions (SUSAR) reporting for the Investigational Medicinal Product (IMP) in accordance with global and local guidelines.

Adverse Event Severity and Relationship to Study Drug

The investigators will rate the severity of each adverse event as mild (grade 1), moderate (grade 2), severe (grade 3), or life-threatening (grade 4). The investigator will use the following definitions to assess the relationship of the adverse event to the use of study drug:

Reasonable Possibility – After consideration of factors including timing of the event, biologic plausibility, clinical judgment, and potential alternative causes, there is sufficient evidence (information) to suggest a causal relationship.

No Reasonable Possibility – After consideration of factors including timing of the event, biologic plausibility, clinical judgment, and potential alternative causes, there is insufficient evidence (information) to suggest a causal relationship.

Adverse Events Due to Cancer Progression and Progression of the Underlying Cancer

Certain AEs are anticipated to occur in this study population at some frequency independent of drug exposure. Such events include known consequences of the underlying disease or condition under investigation (e.g., symptoms, disease progression). These AEs may occur alone or in various combinations and are considered expected AEs in subjects and for reporting purposes for this protocol. "Disease progression" should not be captured when reporting AEs or SAEs, even if fatal, as disease progression will be captured as efficacy outcomes in the trial. Rather, symptoms of disease progression should be reported as AEs or SAEs and the distinction on the AE eCRF marked as appropriate.

Deaths Due to Cancer Progression

For SAEs with the outcome of death, the date and cause of death will be recorded on the appropriate eCRF. Further details are provided in the Operations Manual, Section 4.1.

Pregnancy

Pregnancy in a study subject must be reported to AbbVie within 1 working day of the site becoming aware of the pregnancy. Subjects who become pregnant during the study must discontinue study drug.

All subjects should be informed that contraceptive measures (refer to Section 5.2) should be taken throughout the study and for at least 6 months after the last dose of study drug. Male subjects should be informed that contraceptive measures should be taken by their female partner.

Information regarding a pregnancy occurrence in a study subject and the outcome of the pregnancy will be collected. In the event of a pregnancy occurring in the partner of an enrolled subject, written informed consent for release of medical information from the partner must be obtained prior to the collection of any pregnancy specific information, and the pregnancy will be followed to outcome.

Pregnancy in a study subject is not considered an AE. The medical outcome for either mother or infant, meeting any serious criteria including an elective or spontaneous abortion, is considered a SAE and must be reported to AbbVie within 24 hours of the site becoming aware of the event.

6.2 Toxicity Management

The management of specific AEs and laboratory parameters is described in the Operations Manual, Section 4.4. For the purpose of medical management, all AEs and laboratory abnormalities that occur during the study must be evaluated by the investigator. The table of clinical toxicity grades modified from the National Cancer Institute (NCI) Common Terminology Criteria for Adverse Events (CTCAE), Version 4.03 (available on the NCI-CTEP home page, https://nciterms.nci.nih.gov) is to be used in the grading of AEs and laboratory abnormalities that are reported as AEs, each of which will be followed to satisfactory clinical resolution.

A potential drug-related toxicity is an AE or laboratory value outside of the reference range that is judged by the investigator or AbbVie to have either "reasonable possibility" or "no reasonable possibility" of relationship to the study drug. Toxicity is deemed "clinically significant" based on the medical judgment of the investigator. Toxicity is defined as any clinically significant grade 3 or 4 study drug-related toxicity observed in 1 or more subjects. Subjects who develop a study drug-related grade 1 or 2 AE or laboratory abnormality may continue study medications.

If a subject experiences clinically significant toxicity during a cycle, administration of the next scheduled cycle should be delayed until recovery. Specific recommendations are provided in the Operations Manual, Section 4.4. In the event of isolated CNS progression during study treatment, rovalpituzumab tesirine may be withheld while a palliative treatment is administered.

Management of Special Toxicity Concerns

Serosal effusions (pleural or pericardial), alone or in combination with generalized or peripheral edema and/or hypoalbuminemia, have been observed with rovalpituzumab tesirine. These events have the potential to be life-threatening (e.g., pericardial tamponade). As prophylaxis, rovalpituzumab tesirine is administered with dexamethasone 8 mg orally BID on Day –1, Day 1 (the day of dosing), and Day 2 of each treatment cycle.

Development of serosal effusion events or worsening from baseline warrants prompt evaluation by the Investigator or designee. In the event of a grade 2 or higher AE in this group (effusions, edema, hypoalbuminemia) thought to be related to rovalpituzumab tesirine, consider administration of systemic corticosteroids, e.g., a tapered regimen of dexamethasone. Alternatively, nonsteroidal therapies for serositis may be considered, as outlined in the Operations Manual, Section 4.4.

Skin toxicity with rovalpituzumab tesirine may consist of photosensitivity as well as other reactions (e.g., palmar-plantar erythrodysesthesia, erythema multiforme). Development of a cutaneous reaction during treatment warrants prompt evaluation by the Investigator or designee. For skin reactions, refer to the Operations Manual, Section 4.4. All events of cutaneous toxicity should be monitored until resolution or return to baseline.

Potential drug-induced liver injuries (DILIs) are defined in the Operations Manual, along with recommendations for management. All occurrences of potential DILIs meeting the defined criteria must be reported as SAEs.

6.3 TEAE Case Definition/Guidance

To further aid in prospectively identifying treatment-emergent adverse events (TEAEs), refer to the general signs and symptoms coinciding or preceding each TEAE as listed below.

Serosal Effusions

Serosal effusions have been observed with rovalpituzumab tesirine treatment, mainly pleural and pericardial effusions. Possible risk mitigation of serosal effusions includes administration of dexamethasone orally at 8 mg BID given on Day –1, Day 1 (the day of dosing) and Day 2 or each cycle. Pleural and pericardial effusions are considered separate important identified risks for rovalpituzumab tesirine.

Details regarding serosal effusion management are provided in the Operations Manual, Section 4.4.

Pleural Effusions

In general, signs and symptoms coinciding with or preceding pleural effusions may include shortness of breath, chest tightness or pain, cough, and/or weight gain. Monitoring for symptoms of pleural effusions, which include worsening dyspnea, chest tightness or pain, or worsening cough, should occur throughout the treatment and post-treatment period.

If pleural effusion is suspected, additional laboratory and imaging studies should occur per institutional guidelines.

Details regarding pleural effusion management are provided in the Operations Manual, Section 4.4.

Pericardial Effusions

In general, signs and symptoms coinciding with or preceding events of pericardial effusion may include shortness of breath, chest tightness or pain, cough, and/or weight gain. Most patients with pericardial effusions reported preceding or concurrent events of pleural effusions. Monitoring for symptoms of pericardial effusions, which include worsening dyspnea, chest tightness or pain, worsening cough, syncope, or palpitations should occur throughout the treatment and post-treatment period. If pericardial effusion is suspected, additional laboratory and imaging studies including echocardiography should occur per institutional guidelines. Pericardial effusions can result in cardiac tamponade and can be life-threatening.

Details regarding pericardial effusions management are provided in the Operations Manual, Section 4.4.

Generalized Edema

Generalized edema (anasarca) is considered an important identified risk for rovalpituzumab tesirine. In general, signs and symptoms coinciding with or preceding generalized edema may include generalized swelling including extremities or puffiness of the skin, increased abdomen size, and dyspnea. Generalized edema events are infrequent but have resulted in fatal outcomes and are often preceded by events of peripheral edema. Generalized edema can present as unexplained weight gain, thus monitor for signs and symptoms of fluid retention (using the Fluid Retention Questionnaire [Appendix C of the Operations Manual]). The development of new or worsening edema should prompt evaluation for

associated serosal effusions. Signs and symptoms of generalized edema should be monitored throughout treatment with rovalpituzumab tesirine and as part of the follow up period.

If generalized edema is suspected, additional laboratory and imaging investigation should occur. If generalized edema is confirmed, prompt intervention and treatment is warranted.

Details regarding edema management are provided in the Operations Manual, Section 4.4.

Peripheral Edema

Peripheral edema can present as swelling or puffiness of the skin affecting the legs, feet, and ankles, but it can also involve the arms and face. Peripheral edema can present as unexplained weight gain, and thus it is important to monitor for signs and symptoms of fluid retention (using the Fluid Retention Questionnaire [Appendix C of the Operations Manual]). Regular physical examinations should be conducted during treatment, and the development of new or worsening edema should prompt evaluation for associated serosal effusions or generalized edema.

If peripheral edema is suspected, additional laboratory and imaging investigation should occur per institutional guidelines. If peripheral edema is confirmed, please refer to toxicity management section of the Operations Manual, Section 4.4 for dose reduction instructions.

Cutaneous Reactions

Skin reactions have been reported in almost half of the subjects treated with rovalpituzumab tesirine. Most skin reactions consist of photosensitivity reactions, rash, and erythema and mainly occur in sun-exposed regions like the face and arms. Most cutaneous reactions are ≤ grade 2 and do not require intervention. If not clinically consistent with photosensitivity, the cutaneous reaction should be evaluated by a dermatologist, including consideration for skin biopsy to characterize the reaction and guide subsequent treatment and/or disposition of rovalpituzumab tesirine dosing. Development of a cutaneous reaction during treatment with rovalpituzumab tesirine warrants prompt evaluation.

Details regarding cutaneous skin management are provided in the Operations Manual, Section 4.4.

Photosensitivity

Photosensitivity reactions are an important identified risk for rovalpituzumab tesirine. Photosensitivity is characterized by an increase in sensitivity of the skin to sunlight. Minimization measures and management of photosensitivity are included the Operations Manual, Section 4.4. Rovalpituzumab tesirine associated photosensitivity causes redness (erythema) and sunburn-like appearance of the skin. Typical locations include face, v-shaped area of the neck, dorsal arms and legs. Time to onset of photosensitivity varies widely and may occur hours to days after sun exposure.

Details regarding photosensitivity management are provided in the Operations Manual, Section 4.4.

Thrombocytopenia with Bleeding Events

Thrombocytopenia has been observed with rovalpituzumab tesirine. The majority of thrombocytopenia and platelet count decrease observed with rovalpituzumab tesirine have been ≤ grade 3, are asymptomatic, and not associated with an increased risk of bleeding. In general, signs and symptoms

coinciding with or preceding thrombocytopenia with bleeding may include blood in urine or bowel movement, headaches, heavy menstrual periods, or new or worsening bruising.

If thrombocytopenia is suspected, additional laboratory monitoring per institutional guidelines may be necessary.

Details regarding thrombocytopenia management are provided in the Operations Manual, Section 4.4.

Pneumonitis

Pneumonitis has been infrequently reported with rovalpituzumab tesirine but has resulted in fatal outcomes. In general signs and symptoms coinciding with or preceding pneumonitis may include new or worsening cough, chest pain and/or shortness of breath, fever, and radiographic changes (ground glass opacities). If pneumonitis is suspected, additional laboratory and imaging investigation per institutional guidelines may be necessary.

6.4 Product Complaints

A product complaint is any complaint related to the biologic or drug component of the product or to the medical device component(s).

For a product this may include, but is not limited to, damaged/broken product or packaging, product appearance whose color/markings do not match the labeling, labeling discrepancies/inadequacies in the labeling/instructions (e.g., printing illegible), missing components/product, device not working properly, or packaging issues.

Product complaints concerning the investigational product and/or device must be reported to AbbVie within 1 business day of the study site's knowledge of the event. Product complaints occurring during the study will be followed up to a satisfactory conclusion.

7 STATISTICAL METHODS & DETERMINATION OF SAMPLE SIZE

7.1 Statistical and Analytical Plans

As this is an extension study, no Statistical Analysis Plan (SAP) will be written; only data and listings will be produced for future use. No interim analysis will be planned and performed.

7.2 Definition for Analysis Populations

One analysis set will be used for the long-term, rollover extension study that will include subjects who signed an informed consent and met all the eligibility criteria, unless specified otherwise.

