3.3 Safety Evaluations

Safety evaluations include adverse event monitoring, physical examinations, echocardiography, vital sign measurements, performance status, and clinical laboratory testing. Adverse events (AEs) will be collected from the time of enrollment until the end of the study. For subjects receiving treatment/retreatment in this study, all AEs regardless of seriousness or causality, will be reported through 70 days after the last dose of treatment. Only treatment-related serious adverse events (SAEs) will be collected post 70 days of the last dose of rovalpituzumab tesirine received in the study. In those subjects in Arm A who are not receiving treatment, only treatment-related SAEs will be collected. The AE reporting windows are described below in the schema.

Adverse Event Reporting

Last rovalpituzumab tesirine dose refers to the last dose received by the subject in either the parent study (Arm A, No Retreatment) or this extension study (Arm A Retreatment or Arm B).

Further details on AE reporting are provided in Section 6.1 and the Operations Manual, Section 4. For statistical analysis provided for study disclosure, refer to Section 7.5.

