4.2 Discussion of Study Design

Choice of Control Group

There is no control group in this extension study.

Appropriateness of Measurements

Standard clinical and laboratory procedures will be utilized in this study. All efficacy measurements in this study are standard for assessing disease activity in subjects with SCLC and other indications from parent rovalpituzumab tesirine studies (e.g., Study SCRX001-006).

Suitability of Subject Population

These are all subjects who were enrolled in rovalpituzumab tesirine treatment studies, but have not yet reached 1 or more endpoints in the parent study at the time of primary analyses. In addition, subjects who were eligible for retreatment based on the criteria written in the parent study will have that opportunity in this study.

All subjects must have received at least 1 dose of rovalpituzumab tesirine in the parent study. In order to receive optional retreatment in Arm A, subjects must meet the below eligibility criteria in Section 5.1.

Selection of Doses in the Study

Subjects who receive treatment in this study will receive rovalpituzumab tesirine at a dose of 0.3 mg/kg on Day 1 of every 6 week treatment cycle. If a subject previously required a dose reduction during the parent rovalpituzumab tesirine study, then that reduced dose will be administered for those with ongoing treatment or those electing retreatment. Dose reductions may also occur during treatment or retreatment. If a subject requires a dose reduction, either in the parent rovalpituzumab tesirine study or this extension study, dose re-escalation is not allowed.

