5 STUDY ACTIVITIES

5.1 Eligibility Criteria

Study Entry Criteria

For both Arms A and B; the eligibility criteria are that a subject has enrolled, participated in, and received at least 1 dose of rovalpituzumab tesirine in a parent study.

Arm A Optional Retreatment Criteria

Additional eligibility criterion for Arm A is that subjects who discontinued the study drug in the parent study have completed the treatment emergent AE reporting window (e.g., 30 days post last dose for Study SCRX001-002).

Subjects who elect optional retreatment in Arm A must meet all of the following eligibility criteria before receiving rovalpituzumab tesirine retreatment. Prior to providing retreatment to subjects, study investigators should consult with the AbbVie Medical Monitor.

Demographic and Laboratory Assessments

- 1. Tolerated their initial 2 doses of rovalpituzumab tesirine
- 2. Achieved clinical benefit from rovalpituzumab tesirine, defined as stable disease or better, and is determined that the subject would potentially benefit from additional treatment

Achieved clinical benefit as defined by stable disease or better and experienced radiographic disease progression at least 12 weeks after last dose of rovalpituzumab tesirine per RECIST 1.1

- 3. Received no other systemic anti-cancer therapy after rovalpituzumab tesirine treatment
- 4. Eastern Cooperative Oncology Group (ECOG) performance status of 0 or 1. See the Operations Manual, Appendix B for conversion of performance status using Karnofsky scales, if applicable
- 5. Minimum life expectancy of at least 12 weeks

- 6. Laboratory values meeting the following criteria within the screening period prior to the first dose of study drug:
 - Absolute neutrophil count (ANC) ≥ 1,500/μL;
 - Platelet count ≥ 75,000/μL;
 - Hemoglobin ≥ 8.0 g/dL;
 - Serum total bilirubin $\leq 1.5 \times$ upper limit of normal (ULN) or $\leq 3 \times$ ULN for subjects with Gilbert's disease;
 - Serum alanine aminotransferase (ALT) and aspartate aminotransferase (AST) ≤ 2.5 × ULN (≤ 5 × ULN if evidence of hepatic involvement by malignant disease);
 - Serum creatinine ≤ 1.5 × ULN or estimated glomerular filtration rate (eGFR)
 ≥ 30 mL/min/1.73 m² as calculated by the 4-variable Modification of Diet in Renal Disease study equation (GFR (mL/min/1.73 m²) = 175 × (serum creatinine [mg/dL])-1.154 × (age [years])-0.203 × 0.742 (if female) × 1.212 (if African American).³

Disease Activity

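### On one reasonable reading, the eligibility condition in Section 7.2 drops a subject retreated in breach of a criterion from the safety and death output; 7.5 should rule this out

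*Combined protocol and SAP*

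**What the plan says.** Section 7.2 sets up one analysis set, which "will include subjects who signed an informed consent and met all the eligibility criteria, unless specified otherwise". No safety or as-treated set is defined anywhere.

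Section 5.1 uses the word eligibility at three levels:

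- Study entry: "For both Arms A and B; the eligibility criteria are that a subject has enrolled, participated in, and received at least 1 dose" of the drug in a parent study.
- One further Arm A condition: "Additional eligibility criterion for Arm A is that subjects who discontinued the study drug in the parent study have completed" the parent study's AE reporting window.
- Retreatment: "Subjects who elect optional retreatment in Arm A must meet all of the following eligibility criteria before receiving rovalpituzumab tesirine retreatment". Thirteen numbered items follow.

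Section 4.2 uses the same term for the third level: "In order to receive optional retreatment in Arm A, subjects must meet the below eligibility criteria in Section 5.1". The retreatment screening lists in Appendix D and Operations Manual Section 2.2 do likewise.

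Section 7.5 promises an AE listing, a laboratory listing and descriptive safety summaries for disclosure. Operations Manual Section 4.2 gives counting rules for AEs, and Section 7.3 lists deaths. None of the three names an analysis set or mentions eligibility.

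Section 3.3 ties collection to treatment: "For subjects receiving treatment/retreatment in this study, all AEs regardless of seriousness or causality, will be reported through 70 days" after the last dose. On deviations, Section 5.9 says "If a protocol deviation occurs (or is identified), the Investigator is responsible for notifying IEC/IRB" and other parties, but not how the subject's data are handled. Section 7.1 says that "no Statistical Analysis Plan (SAP) will be written".

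**The concern.** Safety output normally covers everyone who was dosed, whether or not they should have been. Here the only defined population depends on eligibility, while AE collection depends on treatment. If the two differ, data that were collected may not appear in the output.

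The subjects at issue are of interest for safety. Several retreatment items concern blood counts, liver and renal function, and recovery from earlier drug-related toxicity. Safety data on retreated patients are also part of the stated objective (Section 3.1). With no SAP planned, the protocol is the natural place to fix the reading. Otherwise it may be chosen when the output is produced, in an open-label study with the events already known.

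**Working it through.** The plan has no hypothesis, power calculation or sample size, so there is no stated figure to reproduce. The check compares the passages and works out the effect per subject.

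**1. How many conditions are involved (Section 5.1).** Study entry: 1 composite criterion. Additional Arm A criterion: 1. Retreatment: 13 items. Item 6 holds 6 laboratory thresholds (neutrophils, platelets, hemoglobin, bilirubin, ALT/AST, creatinine or eGFR), so the retreatment list contains 12 + 6 = 18 conditions. Not all apply to everyone: item 8 concerns only subjects with CNS metastases, and several contraception items depend on sex.

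**2. What each reading of 7.2 does to a subject retreated in breach of one item.**

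- *Entry criteria only.* The subject stays in. Effect 0.
- *7.2 is a default and 7.5 overrides it.* The subject stays in the 7.5 output. Effect there 0.
- *All criteria that applied to the subject, with no override.* The subject drops out of the AE and laboratory listings and the disclosure summaries. Section 7.3 is equally silent about the set, so the deaths listing follows the same logic.

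**3. Does the text choose between them?** Section 7.5 describes its second disclosure group by treatment, which favours an override. But it does not refer to 7.2 or set eligibility aside, and the same words could describe a subgroup within the 7.2 set. The headings of Section 5.1 separate entry from retreatment, which favours the first reading. But Sections 4.2 and 5.1 both call the retreatment items eligibility criteria, and 7.2 says all. The text does not settle it.

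**4. Can a breach happen?** Section 5.9 foresees deviations. One possible route is that retreatment blood counts and chemistries are listed under central laboratories (Appendix D; Operations Manual Section 2.2), while Operations Manual Section 3.8 lets dosing proceed on local results. A breach could then come to light after dosing. The documents give no rate.

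**5. Effect per excluded subject, on the third reading.**

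- Dosed subjects in the safety output: n becomes n − 1.
- Each preferred term that the subject reported: x becomes x − 1, because Operations Manual Section 4.2 counts a subject once per term. Other terms: x is unchanged.
- Deaths listing: one fewer if the subject died.

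Counts of subjects with an event can therefore only stay the same or fall. If percentages were shown, they could move either way: (x − 1)/(n − 1) is no larger than x/n, but x/(n − 1) is larger than x/n when x is above 0.

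**6. Total effect.** This is the per-subject effect times the number of subjects dosed in breach. Section 7.6 fixes no sample size, and the documents give neither the number retreated nor the number of deviations. No total or percentage range can be given.

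**The case against.** The strongest reply is that the plan already keeps these subjects in. Section 7.2 is only a default, and Section 7.5 describes its output by event, by data collected, by arm or by treatment, never by eligibility. A specific rule normally displaces a default. The entry-only reading is also natural. If 7.2 required all 13 retreatment items of everyone, Arm A subjects who are never retreated would leave the set for failing, say, the performance status item, which would defeat the follow-up objective. The exclusionary reading has to add that only criteria applying to the subject count.

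Much of this stands. A reader might infer that the plan definitely excludes ineligible subjects who were dosed. The documents do not support that, because two sensible readings include them. What remains is that the override and the entry-only meaning must both be inferred.

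A reader might also infer that safety monitoring is compromised. It is not: AE collection follows treatment, and investigators' SAE reporting does not depend on an analysis set. Breaches are also made less likely by the consultation with the medical monitor, the eligibility check before each retreatment period, and the general ban on deviations.

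Nor can the deaths listing be treated as protected while the AE listing is not. Sections 7.3 and 7.5 are equally silent about 7.2, so they stand or fall together.

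**Conclusion.** The point holds as a minor one. Under one reasonable reading of 7.2, a subject retreated in breach of a criterion can be left out of the AE and laboratory listings, the disclosure summaries and the deaths listing.

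An effect needs three things together: the retreatment items count as eligibility criteria in 7.2, Sections 7.3 and 7.5 do not override it, and at least one dosed subject breaches a criterion. The documents establish none of the three. The size is not derivable and may be zero.

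The scope is narrow. No hypothesis test is affected, only listings and descriptive summaries. Arm B is barely affected, because its sole criterion is participation in a parent study with at least one dose there, which subjects entering on ongoing treatment should meet. For Arm A subjects who are not retreated, the same ambiguity could arise only through the entry criterion or the single additional Arm A condition.

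**What to change.** Confine the change to the safety and death output. In Section 7.5, with a cross-reference in 7.2, state that:

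- AE and laboratory output for Arm B and for retreated Arm A subjects includes everyone who received one or more doses of rovalpituzumab tesirine in this extension study, regardless of eligibility deviations;
- the Arm A summary of treatment-related SAEs and the deaths listing in Section 7.3 include every enrolled subject they cover, again regardless of eligibility deviations;
- eligibility deviations are flagged in the listings.

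Leave the reporting windows as they are: the change concerns who is included, not which events. It costs a few sentences and needs no new data. Reported event counts may be slightly less favourable. If the sponsor already intends the inclusive reading, this only writes it down.
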